4.5.3 Management Algorithms for Immuno-Oncology Agents

Immuno-oncology (I-O) agents are associated with adverse events that can differ in severity and duration from adverse events caused by other therapeutic classes. Nivolumab and urelumab are considered immuno-oncology agents in this protocol. Early recognition and management of adverse events associated with immuno-oncology agents may mitigate severe toxicity. Management algorithms have been developed to assist investigators in assessing and managing the following groups of adverse events:

- Gastrointestinal
- Renal
- Pulmonary
- Hepatic
- Endocrinopathies
- Skin
- Neurological

The algorithms recommended for utilization in this protocol are included in [Appendix 3](#).

4.5.4 Guidelines for Dose Modification

Intrasubject dose escalation or reduction of urelumab and nivolumab is not permitted in this study in order to allow better evaluation of extended safety and efficacy at individual dose levels and schedules.

4.5.4.1 Dose Reductions

No dose reductions of either urelumab or nivolumab are permitted in this study.

4.5.5 Dose Delays Due To Toxicity

Subjects who experience a DLT must have study drug held. Subjects who are required to permanently discontinue both study drugs are listed in [Section 4.5.7](#). In addition, all Grade 2 hepatic, pulmonary, renal, gastrointestinal, and neurological adverse events should be evaluated and managed per the toxicity management algorithms (Appendix 3). Subjects not meeting guidelines for permanent discontinuation will be permitted to resume therapy based on the criteria specified below in [Section 4.5.6](#). Subjects eligible to resume study therapy will resume study therapy at the treatment visit following their last received study medication dose.

Depending on the dosing schedule (See [Table 5.1-2](#) and [Table 5.1-5](#)), if there is a delay in dosing of combination dose (same day dose of urelumab and nivolumab) of between 1 -26 days (for subjects receiving the combination dose every 4 weeks), the procedures at the original scheduled visit should be performed as soon as possible. If the delay is more than 26, the visit and dose will be considered missed; the procedures at the next scheduled visit should be performed, and subsequent combination doses will follow at 4.

Depending on the dosing schedule (See [Table 5.1-2](#) and [Table 5.1-5](#)), if there is a delay in dosing of nivolumab of between 1 -12 days, the procedures at the original scheduled visit should be performed as soon as possible. If the delay is more than 12 days, the visit and dose will be considered missed; the procedures at the next scheduled visit should be performed, and subsequent nivolumab doses will follow every 2 weeks.

Whereas the general guidance on dose delays as above will normally apply to all subjects, extensions to the period of dose delays may be granted for individual subjects on a case by case basis after specific consultation and agreement between the investigator and BMS Medical

Monitor in settings where benefit/risk may justify continued study therapy (eg, subject deriving clinical benefit who requires prolonged steroid taper for management of non-DLT drug-related adverse events, or experiences delays for management of a non-drug-related AE).

The end of cycle disease assessments (ie, CT/MRI, PET, etc) will continue on an every 8 weeks schedule relative to the subject's 1st dose regardless of any treatment delay incurred.

4.5.6 Criteria to Resume Treatment

Subjects experiencing AEs not meeting criteria for permanent discontinuation as outlined in [Section 4.5.7](#) may resume treatment with study medication under the following criteria:

- Subjects may resume treatment with study drug when the drug-related AE(s) resolve to Grade ≤ 1 or baseline value with the following exceptions:
 - Subjects may resume treatment in the presence of Grade 2 fatigue;
 - Subjects who have not experienced a Grade 3 drug-related skin AE may resume treatment in the presence of Grade 2 skin toxicity;
 - Subjects with Grade 2 uveitis or eye pain or blurred vision not meeting DLT criteria ([Section 4.5.2](#)) must resolve to baseline prior to resuming study therapy;
 - Drug-related pulmonary toxicity, diarrhea, or colitis, must have resolved to baseline before treatment is resumed;
 - Drug-related endocrinopathies adequately controlled with only physiologic hormone replacement may resume treatment.

NOTE: Subjects who experience a DLT that is considered related only to urelumab may be allowed to continue nivolumab monotherapy following resolution of the event. This will be determined on a case by case basis, after specific consultation and agreement between the investigator and BMS Medical Monitor in settings where benefit/risk may justify continued treatment with nivolumab monotherapy (eg, subjects with asymptomatic, isolated grade 3 ALT and/or AST elevation that responds rapidly to short 2-3 weeks course of steroid therapy).

If the criteria to resume treatment are met, the subject should restart treatment at the next scheduled time point per protocol.

The consideration to re-initiate study therapy under these exceptions will be made on a case by case basis after considering the overall benefit/risk profile and in consultation between the investigator and the study sponsor. Any adverse event with clinical risk will be assessed on a case by case basis with the investigator and the BMS Medical Monitor to determine the risks and benefits of continuing on therapy following resolution versus discontinuing therapy permanently.

If treatment with study medication is delayed > 6 weeks, the subject must be permanently discontinued from study therapy, except as specified in [Section 4.5.7](#)).

4.5.7 Guidelines for Permanent Discontinuation

Subjects will be required to permanently discontinue both study drugs for the following adverse events:

- A. Any drug related AE occurring at any time that meets DLT criteria as outlined in [Section 4.5.2](#) will require permanent discontinuation with the following **exceptions**:
 - a) grade 3 diarrhea, nausea, vomiting, or abdominal pain that returns to grade 1 or baseline within 3 days with medical intervention;
 - b) grade 3 pruritus or rash that returns to grade 1 or baseline within 7 days or baseline with medical intervention;
 - c) grade 4 electrolyte abnormalities that < 72 hours in duration;
 - d) grade 4 neutropenia \leq 7 days in duration;
 - e) grade 4 increase in amylase or lipase that is not associated with clinical or radiographic evidence of pancreatitis;
 - f) grade 4 lymphopenia < 5 days in duration.

NOTE: Subjects who experience a DLT that is considered related only to urelumab may be allowed to continue nivolumab monotherapy following resolution of the event. This will be determined on a case by case basis, after specific consultation and agreement between the investigator and BMS Medical Monitor in settings where benefit/risk may justify continued treatment with nivolumab monotherapy (eg, subjects with asymptomatic, isolated grade 3 ALT and/or AST elevation that responds rapidly to short 2-3 weeks course of steroid therapy).

Any dosing delay lasting > 6 weeks will be cause for permanent discontinuation with the following exceptions:

- Dosing delays to allow for prolonged steroid tapers to manage drug-related adverse events are allowed. Prior to re-initiating treatment in a subject with a dosing delay lasting > 6 weeks, the BMS Medical Monitor must be consulted. Tumor assessments should continue as per protocol even if dosing is delayed.
- Prior to re-initiating treatment in a subject with a dosing delay lasting > 6 weeks, the BMS Medical Monitor must be consulted. Dosing delays > 6 weeks that occur for non-drug-related reasons may be allowed if approved by the BMS Medical Monitor. Whereas the general guidance on dose delays as above will normally apply to all subjects, extensions to the period of dose delays may be granted for individual subjects on a case by case basis after specific consultation and agreement between the investigator and BMS Medical Monitor in settings where benefit/risk may justify continued study therapy (eg, subject deriving clinical benefit who requires prolonged steroid taper for management of non-DLT irAEs, or experiences delays for management of a non-drug-related AE). Tumor assessments should continue as per protocol even if dosing is delayed.

All subjects who discontinue investigational product should comply with protocol specified follow-up procedures as outlined in [Section 5](#). The only exception to this requirement is when a

subject withdraws consent for all study procedures including post-treatment study follow-up or loses the ability to consent freely (ie, is imprisoned or involuntarily incarcerated for the treatment of either a psychiatric or physical illness).

If study treatment is discontinued prior to the subject's completion of the study, the reason for the discontinuation must be documented in the subject's medical records and entered on the appropriate case report form (CRF) page.

4.5.8 *Retreatment with Study Therapy*

The consideration to re-initiate study therapy under these exceptions will be made on a case by case basis after considering the overall benefit/risk profile and in consultation between the investigator and the study sponsor. Any adverse event with clinical risk will be assessed on a case by case basis with the investigator and the BMS Medical Monitor to determine the risks and benefits of continuing on therapy following resolution versus discontinuing therapy permanently.

Subjects who have completed all 6 cycles of treatment and who experience disease progression during the follow-up period after having experienced initial disease control (CR, PR or SD) within 12 months of last treatment with study therapy may be permitted re-initiation of study therapy at their original dose regimen after discussion and agreement with the BMS Medical Monitor. Subjects entering this phase will follow the Time and Events schedule as outlined in [Table 5.1-4](#), [Table 5.1-5](#), and [Table 5.1-6](#). Samples for PK and ADA will be collected as per [Table 5.5.1-3](#), select samples for PD (PBMCs, serum cytokine samples, flow panel samples) will be collected as outlined in [Table 5.7](#).

Subjects undergoing retreatment of study therapy should continue to meet the eligibility criteria with respect to laboratory parameters and organ function at the time study drug resumes and should not have experienced a DLT that would require permanent discontinuation of study therapy.

Screening procedures that need to be repeated are outlined in [Table 5.1-4](#). Subjects will continue to receive study therapy at the same dose levels as assigned at study start. Additional, separate, safety and efficacy listings will be presented for those subjects who reinitiated study therapy.

Subjects who achieve CR during initial therapy and chose to come off therapy for reasons other than toxicity, will be continue to be followed and will be allowed to be re-treated within 12 months of administration of last dose of study drug.

Subjects who experience DLT will not be eligible for retreatment, except as outlined in [Section 4.5.2](#).

4.5.9 *Treatment of Drug Related Infusion Reactions*

Since nivolumab and urelumab contain only human immunoglobulin protein sequences, it is unlikely to be immunogenic and induce infusion or hypersensitivity reactions. However, if such a reaction were to occur, it might manifest with fever, chills, rigors, headache, rash, pruritus, arthralgias, hypo- or hypertension, bronchospasm, or other symptoms. All Grade 3 or 4 infusion reactions should be reported within 24 hours to the BMS Medical Monitor and reported as an SAE if criteria are met. Infusion reactions should be graded according to NCI CTCAE v4.0 guidelines.

Treatment recommendations are provided below and may be modified based on local treatment standards and guidelines as appropriate:

For Grade 1 symptoms: (Mild reaction; infusion interruption not indicated; intervention not indicated)

Remain at bedside and monitor subject until recovery from symptoms. The following prophylactic premedications are recommended for future infusions: diphenhydramine 50 mg (or equivalent) and/or acetaminophen/paracetamol 325 to 1000 mg at least 30 minutes before additional study drug administrations.

For Grade 2 symptoms: (Moderate reaction requires therapy or infusion interruption but responds promptly to symptomatic treatment [eg, antihistamines, non-steroidal anti-inflammatory drugs, narcotics, corticosteroids, bronchodilators, IV fluids]; prophylactic medications indicated for ≤ 24 hours).

Stop the infusion, begin an IV infusion of normal saline, and treat the subject with diphenhydramine 50 mg IV (or equivalent) and/or acetaminophen/paracetamol 325 to 1000 mg; remain at bedside and monitor subject until resolution of symptoms. Corticosteroid or bronchodilator therapy may also be administered as appropriate. If the infusion is interrupted, then restart the infusion at 50% of the original infusion rate when symptoms resolve; if no further complications ensue after 30 minutes, the rate may be increased to 100% of the original infusion rate. Monitor subject closely. If symptoms recur then no further study drug will be administered at that visit. Administer diphenhydramine 50 mg IV, and remain at bedside and monitor the subject until resolution of symptoms. The amount of study drug infused must be recorded on the electronic case report form (eCRF). The following prophylactic premedications are recommended for future infusions: diphenhydramine 50 mg (or equivalent) and/or paracetamol 325 to 1000 mg (acetaminophen) should be administered at least 30 minutes before additional study drug administrations. If necessary, corticosteroids (recommended dose: up to 25 mg of IV hydrocortisone or equivalent) may be used.

For Grade 3 or Grade 4 symptoms: (Severe reaction, Grade 3: prolonged [ie, not rapidly responsive to symptomatic medication and/or brief interruption of infusion]; recurrence of symptoms following initial improvement; hospitalization indicated for other clinical sequelae [eg, renal impairment, pulmonary infiltrates]). Grade 4: (life-threatening; pressor or ventilatory support indicated).

Immediately discontinue study drug infusion. Begin an IV infusion of normal saline, and treat the subject as follows. Recommend bronchodilators, epinephrine 0.2 to 1 mg of a 1:1,000 solution for subcutaneous administration or 0.1 to 0.25 mg of a 1:10,000 solution injected slowly for IV administration, and/or diphenhydramine 50 mg IV with methylprednisolone 100 mg IV (or equivalent), as needed. Subject should be monitored until the investigator is comfortable that the symptoms will not recur. Study drug will be permanently discontinued. Investigators should follow their institutional guidelines for the treatment of anaphylaxis. Remain at bedside and monitor subject until recovery from symptoms. In the case of late-occurring hypersensitivity

symptoms (eg, appearance of a localized or generalized pruritus within 1 week after treatment), symptomatic treatment may be given (eg, oral antihistamine, or corticosteroids).

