4.5.2 Dose Limiting Toxicities

Adverse events will be graded according to the National Cancer Institute (NCI) Common Terminology Criteria for Adverse Events (CTCAE) Version 4.0 (v4.0).

Non-hematologic Dose-Limiting Toxicity (DLT):

A. Hepatic Non-Hematologic DLT

Any one of the following study drug-related events will be considered a hepatic DLT:

- Any \geq grade 3 elevation of AST, ALT or T bili
- Grade 2 AST or ALT with symptomatic liver inflammation (eg, right upper quadrant tenderness, jaundice, pruritus)
- AST or ALT $> 3 \times$ ULN and concurrent total bilirubin $> 2 \times$ ULN without initial findings of cholestasis (elevated serum alkaline phosphatase (ALP) (ie, findings consistent with Hy's law or FDA definition of potential drug-induced liver injury or pDILI)*

*[Note that this special category of DLT uses ULN rather than CTC Grade for definition]

NOTE: Subjects who experience a DLT that is considered related only to urelumab may be allowed to continue nivolumab monotherapy following resolution of the event. This will be determined on a case by case basis, after specific consultation and agreement between the investigator and BMS Medical Monitor in settings where benefit/risk may justify continued treatment with nivolumab

monotherapy (eg, subjects with asymptomatic, isolated grade 3 ALT and/or AST elevation that responds rapidly to short 2-3 weeks course of steroid therapy).

B. Non-Hepatic Non-Hematologic DLT

Any of the following events will be considered a Non-Hepatic Non-Hematologic DLT:

- Any Grade 2 drug-related uveitis or eye pain or blurred vision that does not respond to topical therapy and does not improve to Grade 1 severity within 2 weeks OR requires systemic treatment
- Grade 3 drug-related uveitis, pneumonitis, bronchospasm, neurologic toxicity, hypersensitivity reaction, or infusion reaction of any duration requires discontinuation
- Any Grade 3 or greater non-dermatologic, non-hepatic non-hematologic study drug-related toxicity will be considered a dose-limiting toxicity with the following specific EXCEPTIONS:
 - Grade 3 or grade 4 electrolyte abnormalities that are not complicated by associated clinical adverse experiences, last less than 48 hours and either resolve spontaneously or respond to conventional medical intervention
 - Grade 3 nausea, vomiting or diarrhea that lasts less than 48 hours, and either resolves spontaneously or responds to conventional medical intervention

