 - Isolated Grade 3 elevation of amylase or lipase not associated with clinical or radiographic evidence of pancreatitis
 - Isolated Grade 3 fever not associated with hemodynamic compromise (eg, hypotension, clinical or laboratory evidence of impaired end-organ perfusion)

C. Dermatologic DLT

- Grade 3/4 rash if no improvement (ie, resolution to \leq Grade 1) after a 1-2 week infusion delay. Subjects who have not experienced a Grade 3 drug-related skin AE may resume treatment in the presence of Grade 2 skin toxicity

D. Hematologic DLT (study drug-related)

- Grade 4 neutropenia \geq 7 days in duration
- Grade 4 thrombocytopenia or Grade 3 thrombocytopenia with bleeding, or any requirement for platelet transfusion
- Grade \geq 3 febrile neutropenia for 72 hours
- Grade \geq 3 hemolysis (ie, requiring transfusion or medical intervention such as steroids)
- Grade 4 anemia not explained by underlying disease

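### The electrolyte exception to permanent discontinuation (Protocol 4.5.7 A(c)) names only Grade 4, so some Grade 3 events face a stricter rule than matching Grade 4 events

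*Protocol*

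**What the plan says.** Protocol 4.5.2 B sets the general rule: "Any Grade 3 or greater non-dermatologic, non-hepatic non-hematologic study drug-related toxicity will be considered a dose-limiting toxicity", with specific exceptions. The electrolyte exception covers both grades on one set of terms: "Grade 3 or grade 4 electrolyte abnormalities that are not complicated by associated clinical adverse experiences, last less than 48 hours and either resolve spontaneously". A response to ordinary medical treatment counts in place of spontaneous resolution.

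Protocol 4.5.7 A then makes DLT status the trigger for permanently stopping both drugs: "Any drug related AE occurring at any time that meets DLT criteria as outlined in" section 4.5.2, at any point in treatment, unless one of exceptions (a) to (f) applies. Exception (c) is the only one on electrolytes: "grade 4 electrolyte abnormalities that < 72 hours in duration". Grade 3 electrolyte events appear in none of the six.

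A note in 4.5.2, 4.5.6 and 4.5.7 allows nivolumab monotherapy, case by case and after the event resolves, when the DLT is considered related to urelumab alone.

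**The concern.** The two sections work as a chain: 4.5.2 decides what is a DLT, and 4.5.7 decides which DLTs do not end treatment. For electrolyte events the first link treats Grades 3 and 4 identically and the second does not. The lower grade can therefore fall under the stricter rule, and nothing in the documents says that this is intended.

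The rule is mandatory. Protocol 3.5 lists the 4.5.7 criteria among the reasons for which a subject must stop, and 4.5.4 allows no dose reductions, so sites can only hold, resume or stop. Section 4.5.8 also bars retreatment after a DLT that would require permanent discontinuation. A site applying the text literally could end combination therapy for a Grade 3 event and continue it after a Grade 4 event of the same length. Another site might assume a drafting slip and treat the two alike. Adverse events leading to discontinuation (SAP 7.6.3) and extent of exposure (SAP 7.4) are reported outputs that depend on these decisions.

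**Working it through.** No figure in the plan bears on this point, so the check is of the rules as logic. It covers drug-related Grade 3 or 4 electrolyte events that resolve or respond to treatment.

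Inputs:
- DLT status (Protocol 4.5.2 B): the event is a DLT unless it is uncomplicated and lasts under 48 h.
- Excepted (Protocol 4.5.7 A(c)): Grade 4 and under 72 h, with no condition about complications.
- Permanent stop (Protocol 4.5.7 A): the event is a DLT and is not excepted.

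Results by duration, complication status and grade:

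| Duration | Complicated | Grade 3 | Grade 4 |
|---|---|---|---|
| under 48 h | no | not a DLT, no stop | not a DLT, no stop |
| under 48 h | yes | DLT, permanent stop | DLT, excepted |
| 48 to under 72 h | no | DLT, permanent stop | DLT, excepted |
| 48 to under 72 h | yes | DLT, permanent stop | DLT, excepted |
| 72 h or more | either | DLT, permanent stop | DLT, permanent stop |

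For example, an uncomplicated event of 60 h is a DLT at either grade, because 60 is not under 48. At Grade 3, (c) does not apply, so the subject stops. At Grade 4, 60 is under 72, so (c) applies and the subject is excepted. The grades part company in the three middle rows.

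The neighbouring exceptions show whether this could be a general drafting pattern. Exception (a) also has a longer limit than the DLT list: Grade 3 nausea, vomiting or diarrhea escapes DLT status if under 48 h, and escapes permanent discontinuation if it returns to Grade 1 or baseline within 3 days. So the step from 48 to 72 h in (c) is not an error in itself. But (a) names the grade that 4.5.2 names, and (c) drops one. Exception (e), on Grade 4 amylase or lipase, keeps the requirement of no pancreatitis that 4.5.2 uses, whereas (c) drops its clinical condition. The missing grade and the missing condition are therefore particular to (c).

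**The case against.** The strongest reply is that exception (c) does not give a Grade 4 event free passage. It excepts the electrolyte abnormality only; a drug-related Grade 3 or higher clinical complication may itself be a DLT and trigger 4.5.7 A. Any DLT requires a dose hold (4.5.5). Resumption generally needs resolution to Grade 1 or baseline, and events with clinical risk are reviewed case by case with the Medical Monitor (4.5.6). The investigator must stop treatment when continuing is against the subject's interest (3.5). All of this stands. A reader might infer that complicated Grade 4 events lead straight to rechallenge, and the documents do not support that.

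On the Grade 3 side, the monotherapy note is real but partial relief: it applies only when urelumab alone is implicated, and it does not restore the combination. The case-by-case review in 4.5.6 is framed for events that do not meet the permanent-discontinuation criteria, so it does not clearly reach this subject.

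A reader might also infer that the whole list of exceptions is out of step with the DLT definition. It is not: (a) and (e) fit. The neutropenia lines, a DLT at 7 days or more and exception (d) at 7 days or less, do not contradict each other. An exception is meant to overlap the definition, so at exactly 7 days the event is a DLT excepted from permanent discontinuation. Exception (d) is nearly redundant rather than in conflict. Exception (f), "grade 4 lymphopenia < 5 days in duration", concerns an event that the hematologic DLT list does not contain; it is surplus text and changes no subject's treatment.

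Finally, discontinuations are tabulated and listed by subject (SAP 7.6.3), so affected stops would be visible. The documents do not show that reported safety results would be materially distorted.

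**Conclusion.** The inconsistency holds on the current text. For drug-related electrolyte abnormalities, 4.5.7 A(c) departs from 4.5.2 B in two respects: it omits Grade 3, and it omits the condition about complications. The result is a default permanent stop of both drugs for Grade 3 events of 48 to under 72 h, and for complicated Grade 3 events under 48 h, where the matching Grade 4 event is excepted. The monotherapy note qualifies the first outcome; the hold, the resumption criteria, clinical review, investigator judgement and any separate DLT qualify the second.

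The conclusion assumes a literal reading and events that resolve or respond to treatment. Its practical size cannot be estimated because the documents give no electrolyte event rates. The planned total of up to approximately 260 subjects is the population under the rule, not the number affected, which may be small. Sample size and the descriptive analyses are untouched. The point matters because a mandatory stopping rule is inconsistent as written and is cheap to correct.

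**What to change.** Reconcile Protocol 4.5.7 A(c) with 4.5.2 B. The revised text should state which grades the exception covers and whether the condition about complications applies. If the difference between 48 and 72 hours, or between the grades, is intended, it should say so. Copying the 4.5.2 terms unchanged into (c) would leave it with no effect, since it would then cover only events that are not DLTs. The clinical limits are for the sponsor's clinicians, and no view is offered here on which passage is right.

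Exceptions (d) and (f) can be tidied in the same edit, as editorial matters only. The cost is wording in the protocol, with no new assessments and no change to the analysis.
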